Appendix B: Rules for Censoring in Time to Event Analyses

Below are the detailed rules for determining the time of the event and the censoring times for the various time-to-event analyses to be performed for this study.

Time-to-Event Variable	Event Time Point	Censor Time Point
Time to achieve a 50% reduction of baseline pain	The first time point where pain half gone is indicated, prior to the use of any rescue medication.	Subjects without events are censored at the earlier of the time of their first use of rescue medication and the time of their last, non-missing pain half gone assessment.
Time to onset of first perceptible pain relief*	The time when perceptible pain relief stopwatch is stopped, prior to the use of any rescue medication.	Subjects without events (as indicated by checking the “no” perceptible pain relief box or taking rescue medication prior to the occurrence of perceptible pain relief) are censored at the earlier of the time of their first use of rescue medication, the minutes/seconds entered for time of perceptible pain relief (which is when the stopwatch was stopped and so no longer assessed), and 8 hours.
Time to onset of meaningful pain relief*	The time when meaningful pain relief stopwatch is stopped, prior to the use of any rescue medication.	Subjects without events (as indicated by checking the “no” meaningful pain relief box or taking rescue medication prior to the occurrence of meaningful pain relief) are censored at the earlier of the time of their first use of rescue medication, the minutes/seconds entered for time of meaningful pain relief (which is when the stopwatch was stopped and so no longer assessed), and 8 hours.
Time to intake of first rescue medication dose	The time of first intake of rescue medication within 24 hours of first dose.	Subjects without events are censored at the time of their 24 hour global assessment (at the time when rescue meds were to be turned in), and if one did not take place, then at 24 hours (i.e., when subjects were to turn in their unused rescue medication as Visit 3).
Time to request the first dose of rescue medication	The time of the first request for rescue medication within 24 hours of first dose.	Subjects without events are censored at the time of their 24 hour global assessment (at the time when rescue meds were to be turned in), and if one did not take place, then at 24 hours (i.e., when subjects were to turn in their unused rescue medication as Visit 3).
Time to peak pain relief score	The first time point where the subject experiences their peak pain relief score among assessments made prior to use of any rescue medication.	All subjects with post-baseline assessments have events – there is no censoring.
Time to peak pain intensity difference score	The first time point where the subject experiences their peak pain intensity difference score, among assessments made prior to use of any rescue medication.	All subjects with post-baseline assessments have events – there is no censoring.

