Subjects requiring fourth molar extraction are allowed in the trial. Subjects with molars linked to the mandibular canal and those requiring immediate dental procedures other than third and fourth molar extraction must not be included in the trial.

Postoperative baseline examination and treatment allocation

After surgery, subjects will assess their pain on an 11-point NRS. Subjects who report at least moderate baseline pain intensity (≥ 5 on the NRS) within 4 hours after surgery will be allocated to treatment. If 4 hours elapse without the development of moderate to severe dental pain following the completion of surgery, subjects must not be allocated and must be discontinued from the trial.

The first dose of the IMPs (1 capsule or tablet with active treatment plus 3 placebos) will be administered as soon as subjects report a pain intensity ≥ 5 on the NRS. The time of dosing will be recorded. The use of cold compresses or ice bags on the cheeks of subjects is allowed 4 hours after the administration of IMP; their use must be avoided in the 30-minute period before each pain assessment.

Subjects who undergo surgery and receive IMPs will stay in the dental clinic or other research facility for at least 8 hours after the initial dose and will receive the second dose of IMPs at 8 hours (± 10 minutes). If pain assessments will take place in other research facilities, subjects must be transported to the facility between 15 minutes after the end of surgery and the first IMP administration; the commuting time may be up to 30 minutes. During transfer, subjects must be accompanied by a member of the SMO staff. Both must have written directions in the case of emergency.

Thereafter, they can leave the site and take their third dose of IMPs at home 16 hours (± 1 hour) after the first dose of IMPs. They will be asked to document the intake time and to return for Visit 3 the next day at a time which allows a pain assessment 24 hours after the initial IMP dose was given.

At the site, subjects will be provided with 2 stopwatches and a pain assessment booklet. They will be asked to record their pain assessments during the following 8 hours as follows.

- The baseline pain intensity score (11-point NRS) before the first dose of IMPs (Section 12.2.1.1).
- Pain intensity scores at 15, 30, 45, 60, and 90 minutes (± 2 minutes), and at 2, 3, 4, 5, 6, 7, 8 hours (± 6 minutes) after the first dose of IMPs (Section 12.2.1.1).

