- Pain relief on a 5-point VRS at 15, 30, 45, 60, 90 minutes (± 2 minutes), and at 2, 3, 4, 5, 6, 7, and 8 hours (± 6 minutes) after administration of the first dose of IMPs (Section 12.2.1.2).
- Stopwatch 1: subject documents the moment she/he feels the onset of first perceptible pain relief (Section 12.2.1.5).
- Stopwatch 2: subject documents the moment she/he feels the time to onset of a meaningful pain relief (Section 12.2.1.5).
- Response to the question if pain is at least half gone (see Section 12.2.2).

A summary of scheduled procedures for the Allocation Visit (Visit 2) is as follows:

- Check if any of the exclusion criteria for Visit 2 apply (see Section 1.3.2.2).
- Check availability of results of clinical laboratory parameters (to assess Inclusion Criterion 4 if not done before).
- Perform a radiological examination of the affected third molars and document the impacted ones if not done previously (see Section 12.1.5.4).

-
- Collect a urine sample and perform a pregnancy test in female subjects with childbearing potential (see Section 12.1.5.3).
 - Measure and record the subject's vital signs (pulse rate, systolic and diastolic blood pressure, and respiratory rate) (see Section 12.3.2).
 - Record the subject's prior medication stopped before surgery and any concomitant medication (see Section 12.1.2).
 - Monitor the subject for and record any adverse event that occurred during or after the surgery (see Section 12.3.1).
 - Instruct the subject on how to complete the pain assessments following surgery.
 - Hand out stopwatches and a pain assessment booklet (NRS).
 - Reinforce instructions regarding procedures for completion of the pain assessments.
 - Administer IMPs immediately after the baseline pain assessment and record time.
 - Commence time monitoring using the stopwatches provided for first perceptible and meaningful pain relief immediately upon IMP administration.
 - Collect the pain assessment booklet and stopwatches before the subject leaves the clinic and transcribe the subject-reported data to the CRF.
 - Ask the subject to perform a global evaluation of the treatment they received (5-point Likert scale) before the subject leaves the clinic, i.e., 8 hours after first IMP intake or before the first intake of rescue medication (whatever the first).
 - Handout IMPs to be taken 16 hours (± 1 hour) after first IMP dose to cover 24 hours of treatment.

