9.3 Secondary Efficacy Analyses

The analysis of the following list of the secondary endpoints is given below:

1. Total Pain Relief at 6 hours (TOTPAR6), 8 hours (TOTPAR8) post-dose
2. Summed Pain Intensity Difference (SPID) at 4, 6, 8, and 24 hours after first dose
3. Time to achieve a 50% reduction of baseline pain (pain at least half gone)
4. Time to onset of first perceptible pain relief (stopwatch 1)
5. Time to onset of meaningful pain relief (stopwatch 2)
6. Time to intake of first rescue medication dose
7. Subject's global evaluation of the treatment (5-point Likert Scale; 0 poor to 4 excellent) at 8 hours after the first dose of IMPs or before first intake of rescue medication (whichever was first) and at 24 hours after the first dose of IMPs

TOTPARs and SPIDs at each of their summary time points will be analyzed using the same ANCOVA model described for the primary endpoint. Note that alpha levels for secondary analyses are not adjusted for multiple comparisons.

The time to onset of event endpoints will be presented using Kaplan-Meier plots. Medians will be compared across the groups using Wilcoxon Log-rank test, and Hazard Ratios (HR) will be compared across the groups using Cox Hazard Ratio model. Time to onset will be defined as date/time from the first administration of IMPs to the date/time when the subject first reports the event (50% reduction of baseline pain, perceptible pain relief, meaningful pain relief, and intake of rescue medication – each separately). The summaries will include quartiles and HR and their corresponding 95% confidence intervals. Please see [Appendix B](#) for details on the determination of event and censoring time points.

Note that alpha levels for secondary analyses are not adjusted for multiple comparisons.

Subject's global assessment of the treatment will also be summarized with descriptive statistics (patient counts and percentages for each assessment category) at 8 and 24 hours.

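### The stopwatch rows of SAP Appendix B cap non-events at 8 hours but set no visible cap on events, so a single later stop takes that arm's Kaplan-Meier curve to 100% onset

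*SAP*

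**What the plan says.** SAP Appendix B has one row for each stopwatch endpoint. The event for first perceptible relief is "The time when perceptible pain relief stopwatch is stopped, prior to the use of any rescue medication"; for meaningful relief it is "The time when meaningful pain relief stopwatch is stopped, prior to the use of any rescue medication". Neither event definition names a latest time.

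The censoring column of both rows takes the earliest of three times for a subject without onset: first rescue use, the reading entered for the watch, and a fixed limit. The list ends "which is when the stopwatch was stopped and so no longer assessed), and 8 hours". No censored time can therefore exceed 8 hours.

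The row for rescue intake in the same table does bound its event: "The time of first intake of rescue medication within 24 hours of first dose".

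Both stopwatch rows carry an asterisk. The footnote it points to is not in the extracted text.

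On conduct, Protocol 11.1.2.1 sets the recording period: "They will be asked to record their pain assessments during the following 8 hours as follows". It also keeps treated subjects on site "for at least 8 hours after the initial dose and will receive the second dose of IMPs at 8 hours", with a tolerance of 10 minutes either way on that dose. For the watches it says: "Collect the pain assessment booklet and stopwatches before the subject leaves the clinic".

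SAP 9.3 presents these endpoints as Kaplan-Meier plots and adds: "The summaries will include quartiles and HR and their corresponding 95% confidence intervals". Figures 14.2.10.7 and 14.2.10.8 and Tables 14.2.8.2 and 14.2.8.3 are reserved for them.

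**The concern.** Within one row, events and non-events are followed over different windows. Take two subjects whose watches both read 8 h 05 min, neither rescued. The one who marks no relief is moved back to 8 h and censored; the other is an event at 8.08 h. Past 8 h the risk set holds only people already known to have an event, which breaks the logic of the product-limit estimate.

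Such a stop is possible. The second dose may be given on site up to 8 h 10 min, and the watches are collected before departure rather than at 8 h exactly.

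At stake is how two secondary endpoints are described. An arm with one late stop would appear to reach complete onset, while an arm without one would show its true plateau on the same figure. In a weak arm, a quartile that should be reported as not reached could appear as a number.

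**Working it through.** **Inputs from the documents.** Event and censoring rules: SAP Appendix B. Arm size: 180 evaluable per arm (SAP 4), which gives 180/(1 − 0.10) = 200 allocated. The plan states no onset rate, median or quartile for the stopwatch endpoints, so there is no figure of its own to reproduce.

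**Assumptions.** Onset in 15% to 90% of an arm, rescue before onset in 5% to 60%, and one late stop at 8 h 05 min (8.08 h). In the table below, onsets were drawn uniformly over 0.25 to 6 h and rescues over 1 to 6 h.

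**Step 1: end of the curve.** Let S(8) be the Kaplan-Meier proportion without onset at 8 h, and L the number of late stoppers. A late stopper is at risk up to 8 h under either rule, so S(8) is the same under both. After 8 h the risk set is L, and each stop multiplies S by (1 − 1/number at risk).

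- L = 1: S = S(8) × (1 − 1/1) = 0.
- L = 2: S = S(8) × (1 − 1/2) × (1 − 1/1) = 0.

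The last factor is always zero, so the curve ends at 100% onset. This happened in all 21 configurations run.

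**Step 2: quartiles.** A quartile is the first time S falls to 0.75, 0.50 or 0.25. If it was reached by 8 h it cannot change. If not, it now falls on a late stop. Results for n = 180 (times in hours; NR = not reached):

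| Onset / rescued / censored at 8 h / late stop | Onset at 8 h | Q1, median, Q3 as written | Q1, median, Q3 with common 8 h limit |
|---|---|---|---|
| 27 / 108 / 44 / 1 | 22.2% | 8.08, 8.08, 8.08 | NR, NR, NR |
| 63 / 90 / 26 / 1 | 52.6% | 3.98, 5.75, 8.08 | 3.98, 5.75, NR |
| 90 / 54 / 35 / 1 | 63.9% | 3.22, 5.02, 8.08 | 3.22, 5.02, NR |
| 126 / 18 / 35 / 1 | 76.4% | 2.50, 4.27, 5.80 | unchanged |
| 144 / 18 / 17 / 1 | 86.3% | 2.22, 3.62, 5.13 | unchanged |
| 162 / 9 / 8 / 1 | 94.1% | 1.93, 3.39, 4.70 | unchanged |

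The threshold is clearest without rescue, with onsets spaced evenly from 0.3 to 6 h. With 134/180 = 74.4% onset, Q3 prints at 8.08 h. With 136/180 = 75.6%, Q3 is 5.96 h and correct.

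**Step 3: comparisons between arms.** Two arms of 180 were compared, one with 55% onset and 35% rescue, the other with 45% and 40%.

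- Late stop in one arm only: at that time one person is at risk, so observed minus expected is 1 − 1 × 1/1 = 0. Log-rank (5.238), Gehan-Wilcoxon (3.146) and hazard ratio (1.408) are identical under both rules.
- One late stop in the first arm and two in the second, all at 8.08 h: the hazard ratio is 1.400 as written and 1.408 with the common limit; the two test statistics do not change. Staggered stops would add terms from risk sets of two or three people, which is little beside the rest of the data.

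**The case against.** The strongest answer is that the plan may already contain the limit. Both rows carry an asterisk and the note is not in the extracted text; it could cap the event. This stands, and it is the first thing to check.

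Second, the protocol sets an 8-hour recording period and lists both stopwatches within it. The 8-hour global evaluation is also tied to departure. Read that way, a later stop falls outside planned recording. That shows the intent and makes late stops unlikely to be many, but it does not say what the analysis does with one. The dose tolerance and collection at departure leave some minutes in which one can occur.

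Third, a reader might infer that any late stop prints a false quartile, or that the treatment comparison is biased. The calculations support neither. At 76.4% onset or more in the table, all three quartiles were correct, and the tests and hazard ratio barely moved. SAP 9.3 also leaves secondary analyses without multiplicity adjustment, and TOTPAR4 is untouched.

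**Conclusion.** The mismatch is present in the visible text of both stopwatch rows. Given one pre-rescue stop after 8 h that is counted as an event, the false 100% endpoint is certain. The false quartile is conditional on Kaplan-Meier onset by 8 h below 75% (third quartile), 50% (median) or 25% (first quartile). Without a late stop there is no effect.

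How often this would arise cannot be derived: the documents give neither onset nor late-stop rates, and those used above are assumptions. The effect is confined to the tail of a curve and to unreached quartiles of two secondary endpoints. Severity is minor, subject to the missing footnote.

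**What to change.** First check the footnote behind the asterisk. If it already limits events to 8 hours, confirming that is enough.

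Otherwise, in both rows, define the event as a stopwatch stopped no later than 8 hours after first dose and before any rescue medication. Add that a later stop is a non-event, censored at 8 hours. This matches the protocol's recording period and should be settled before unblinding.

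The cost is one sentence in each of two SAP rows, with no new data. The downside is that a few onsets recorded shortly after 8 h will be shown as not reached by 8 h. No separate change to the figure axes is needed, because nothing then lies beyond 8 h.

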 - Hand out sufficient rescue medication (ibuprofen 400 mg) to cover 24 hours of treatment of dental pain if insufficiently resolved by the intake of IMPs.
 - Hand out an information sheet to the subject with the protocol directions and contact details.
 - Hand out a booklet and ask the subject to document at home:
 - Pain intensity and pain relief at 16 hours.
 - The intake of the third dose of IMPs.
 - Any use of rescue medication.
 - Any use of other medication.
 - Adverse events they might experience.
 - Check that the subjects are in a condition to leave the site.
 - Before subjects leave the site they should be reminded that tramadol-containing products, may impair the mental and/or physical abilities required for the performance of potential hazardous tasks such as driving a car or operating machinery.
 - Ask the subject to come to the site on the next day at a pre-set time (24 hours after first IMP intake) for Visit 3.

Dental clinics must have an emergency kit according to local regulations (Norma Oficial Mexicana NOM-005-SSA3-2010). An emergency crash cart will be mandatory at each research facility any time an IMP is being administered.

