13.2 Subject reported outcomes

Subject's pain assessments (NRS), pain relief scores, responses to the question if pain is at least half gone, and IMP/rescue medication intake at home will be captured by paper.

All subject reported outcomes reported on paper will stay as source data at the trial site. The investigator is responsible for the accurate transfer of these data into the CRFs (see Section 13.1).

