2. STUDY OBJECTIVES

The primary objective is:

1. To demonstrate the analgesic efficacy of the tramadol HCl/diclofenac sodium fixed dose combination (FDC) at 2 dose levels (50 mg/50 mg, 25 mg/25 mg) in comparison to the monotherapy of diclofenac sodium 50 mg and tramadol HCl 50 mg. The primary endpoint is pain relief expressed as Total Pain Relief over the 4 hours post-dose period (TOTPAR4).

The specific primary objective breaks down to demonstrating the following:

1. Either tramadol HCl/diclofenac sodium 50 mg/50 mg FDC has superior analgesic efficacy than monotherapy with diclofenac sodium 50 mg,
2. Or tramadol HCl/diclofenac sodium 50 mg/50 mg FDC has superior analgesic efficacy than monotherapy with tramadol HCl 50 mg,
3. Or tramadol HCl/diclofenac sodium 25 mg/25 mg FDC is not inferior to monotherapy with tramadol HCl 50 mg,
4. Or tramadol HCl/diclofenac sodium 25 mg/25 mg FDC is not inferior to monotherapy with diclofenac sodium 50 mg.

The secondary objectives are:

1. To further explore the efficacy of the tramadol HCl/diclofenac sodium FDC at 2 dose levels (50 mg/50 mg, 25 mg/25 mg) in comparison to the monotherapy of diclofenac sodium 50 mg and tramadol HCl 50 mg. The endpoints include:
 - a) Total Pain Relief at 6 hours (TOTPAR6), 8 hours post-dose (TOTPAR8)
 - b) Summed Pain Intensity Difference (SPID) at 4, 6, 8, and 24 hours post-dose
 - c) Time to achieve a 50% reduction of baseline pain (based on the question: *“My starting pain is at least half gone”* Yes/No)

- d) Time to onset of first perceptible pain relief (based on the stopwatch question: *“I would like you to stop the stopwatch when you first feel any pain relief whatsoever. This does not mean you feel completely better, although you might, but when you first feel any difference in the pain that you have had.”*)
 - e) Time to onset of meaningful pain relief (based on the stopwatch question: *“I would like you to stop the stopwatch when you have meaningful pain relief. That is, when the relief is meaningful to you.”*)
 - f) Time to intake of first rescue medication dose
 - g) Time to request the first dose of rescue medication
2. To compare the overall impression of the subject on the treatment they received. The endpoint is subject’s global evaluation of the treatment (5-point Likert Scale) 8 hours or before first intake of rescue medication (whichever was first) and 24 hours after the first dose of Investigational Medicinal Products (IMP).

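### SAP Appendix B has no rule for a first rescue dose taken at home without a recorded request, so such a subject would be censored as request-free to about 24 hours

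*SAP*

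**What the plan says.** **Event and censoring.** The time-to-request row of SAP Appendix B defines the event as "The time of the first request for rescue medication within 24 hours of first dose". For the rest, "Subjects without events are censored at the time of their 24 hour global assessment", or at 24 hours if that assessment did not take place. The intake row has the same censoring rule, but its event is "The time of first intake of rescue medication within 24 hours of first dose".

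**Setting.** Protocol 11.1.2.1 keeps treated subjects on site "for at least 8 hours after the initial dose". Before they leave, staff are to "Hand out sufficient rescue medication (ibuprofen 400 mg) to cover 24 hours of treatment of dental pain".

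**Home records.** In the same section, the rescue item in the list of things to document at home is "Any use of rescue medication". Protocol 13.2 says that "IMP/rescue medication intake at home will be captured by paper".

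**Request times generally.** The schedule of events (Protocol 1.8) marks rescue request and intake at Visit 3 as well as Visit 2. Protocol 10.5 and 12.2.4 and SAP Appendix A item 11 call for the request time, with no restriction to the site.

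**Missing values.** SAP 8.3 allows imputation only for TOTPAR4, TOTPAR6 and TOTPAR8. All other endpoints keep their missing values.

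**Tier.** SAP 2 lists "Time to request the first dose of rescue medication" under the secondary objectives (item g). SAP 8.1.3 and 9.4 place it among the additional or exploratory outcomes.

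**The concern.** The request endpoint follows subjects for 24 hours, but for up to about 16 of those hours (24 − 8) they may be at home with their own supply and no staff member to ask. Appendix B does not say how a first rescue dose taken there enters the analysis. If no request time was recorded, the subject falls into the group without events and is censored at about 24 hours, although the database shows rescue use before then.

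Two things are at stake. First, the request curve could overstate the share of subjects who got through 24 hours without needing rescue, and it could disagree with the intake curve for the same subjects. Both curves are planned outputs (Tables 14.2.8.4 and 14.2.8.5, Figures 14.2.10.9 and 14.2.10.10). Second, any difference between arms in home rescue would drop out of the request comparison to the extent that request fields are blank. With no rule, the handling depends on how each site fills in the field.

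**Working it through.** The plan states no figure for this endpoint, so there is nothing to reproduce. The check compares the rules and then illustrates the possible size.

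**Step 1: follow one subject through the rules.** Take a subject with no rescue on site and a first ibuprofen dose at home at 12 hours.

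- Time to intake: event at 12 hours.
- Time to request, request time recorded: event at that time.
- Time to request, no request time recorded: no event, so censored at the 24-hour global assessment or at 24 hours.

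In the third case, SAP 8.3 stops the programmer from using the intake time in place of the blank. SAP Appendix A item 11 does not help: it covers request and intake together but derives only the time to the first rescue dose.

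**Step 2: compare with the neighbouring rows.** Appendix B caps both stopwatch endpoints at 8 hours, and Protocol 11.1.2.1 has the stopwatches collected before subjects leave. There the follow-up matches the period in which the measurement is made. The request endpoint runs to 24 hours without such a match.

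**Step 3: illustrate the size.** The documents give no rescue rates, so these are assumptions:

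- n = 200 allocated per arm (SAP 4).
- p8 = share first rescued on site by 8 hours, each with a recorded request: 0.2 to 0.6.
- q = share of the remainder first rescued at home by 24 hours: 0.1 to 0.4.
- Every home request field is blank, and nobody is lost before 24 hours.

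Formulas:

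- Intake incidence at 24 hours = p8 + (1 − p8) × q
- Request incidence at 24 hours as written = p8
- Subjects per arm classified differently = 200 × (1 − p8) × q

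| p8 | q | Intake by 24 h | Request by 24 h | Subjects per arm |
|---|---|---|---|---|
| 0.6 | 0.1 | 64% | 60% | 8 |
| 0.4 | 0.2 | 52% | 40% | 24 |
| 0.2 | 0.4 | 52% | 20% | 64 |

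For the middle row: 0.4 + 0.6 × 0.2 = 0.52, and 200 × 0.6 × 0.2 = 24. In that row the median time to intake falls within 24 hours, while the median time to request is not reached. If sites enter a request time for every home dose, the last column is 0 throughout.

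**The case against.** The strongest reply is that the plan does ask for request times. The Visit 3 entry in the schedule of events covers request as well as intake, and Visit 3 is when home data are transferred to the CRF. Protocol 12.2.4 makes documenting the request time mandatory, and neither it nor 10.5 limits this to the site. The booklet and CRF pages are not in the documents, and the list in Protocol 11.1.2.1 may not show every field. Protocol 13.3 provides automatic queries for missing data and inconsistencies, and SAP 5.6 allows a blinded review of missing or partial dates if needed.

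Most of this stands. A reader might infer that home rescue has no request step and that everyone first rescued at home is therefore censored. The documents do not say so: the problem arises only where the request time is blank. The reply does not remove the gap, though. It shows a duty to record a request time, but no listed home item that supplies one, and no definition of what a request means for someone holding the tablets. Queries can prompt an entry but do not define it.

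It is also fair that home rescue is not lost to the trial. Time to first intake, a secondary endpoint, counts it as an event up to 24 hours. Request and intake are different variables, and their curves may differ legitimately on site. The time-to-request endpoint is peripheral: Protocol 1.2 does not list it as secondary, Protocol 14.5.4 has it among additional outcomes, and SAP 9.4 makes no multiplicity adjustment.

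Two further inferences are not supported. One is that home rescue marks the wearing-off of the first two doses. Protocol 8.1 and 12.4 place the fall of comparator concentrations below effective levels at about 4 hours, which is on site, and a third dose is scheduled at home at 16 hours. The other is that a treatment contrast is biased by a known amount. Nothing in the documents gives home rescue rates by arm.

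**Conclusion.** The point holds as a gap in the derivation rule. Appendix B, read together with SAP 8.3, would score a subject who took rescue at home without a recorded request as request-free to about 24 hours, in contradiction to the intake analysis. How often this would occur cannot be determined from the documents. The range of 8 to 64 of 200 per arm rests on assumed rates and on every home request field being blank, and the lower bound in practice is 0.

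The primary tests, the Holm procedure and the time-to-intake analysis are unaffected. This is an inexpensive improvement to an effectively exploratory endpoint, worth making because a table and a Kaplan-Meier figure will report it. The differing tier in SAP 2 is a separate editorial mismatch.

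**What to change.** Before unblinding, change the time-to-request row of SAP Appendix B so that the event time is the earlier of the first recorded request and the first rescue intake, within 24 hours of first dose. Add a note to SAP 8.3 that this derivation is an exception to its no-imputation sentence.

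Alternatively, restrict the endpoint to the on-site period, with censoring at site departure. The documents list no recorded departure time, so a fixed 8-hour cut-off, as for the stopwatch endpoints, may be easier to program.

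Editorially, align SAP 2 item (g) with SAP 8.1.3 and 9.4 so that the endpoint has one tier.

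The cost is one sentence in Appendix B, one exception in SAP 8.3 and one derivation line. The first option needs no new data, because rescue intake is already collected. Its small downside is that request and intake times coincide for home rescue. The second option avoids that but gives up the request endpoint after the site period, where the intake analysis still applies.
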